## 2.1 Experience and Training in Human Research ethics

✓ corporate in post-graduate curriculum

## 4. Background & Rationale

There was high incidence of shoulder pain in population with occupationally related to repetitive overhead position or work in the awkward position. This was evident especially when involving with sustained shoulder rotation position, lifting heavy loads or using vibratory tools. The shoulder pain was reported to be the third most common problem reported on musculoskeletal disorder after back and knee pain, approximately 16% to 21% of the population. Its prevalence in persons 60 years and older is 34%.

MU-CIRB	Mahidol University Central Institutional Review Board (MU-CIRB)	Date Modified 02/08/2016
Mahidol University Centra	ll Institutional Review Board (MU Central-IRB) Study Protocol	Page 2 of 13

Based on the literature review, shoulder function is related to the postural problem and scapulo-humeral kinematics. The main mechanism of shoulder impingement syndrome is related to the narrowing of subacromial space which leads to a compressive and shear forces to the structures below that space.

The common intervention of the shoulder impingement syndrome is conventional physical therapy that consists of stretching, modality, education and passive mobilization. Manual therapy and exercises are necessary to treat the patient with the shoulder impingement syndrome. Specific exercises focus on the biomechanical aspect such as postural correction exercise.

The current manual therapy technique, the mobilization with movement which is posterolateral glide using the treatment belt, might help the physical therapist give more stable pull action, while the other hand on the scapula to assist the movement and give a direction of proper biomechanics. Some studies showed different results and limitation of the method of applying the mobilization with movement technique. Previous studies investigated the effects of mobilization with movement in the patients with shoulder dysfunction and/or shoulder impingement syndrome. A case report conducted by DeSantis and Hasson applied the mobilization with movement, other manual therapy, modalities, and therapeutic exercise to a male patient with shoulder impingement syndrome. The results showed that the mobilization with movement may be an effective treatment intervention for the patient.

Another study conducted by Tey et al evaluated the immediate effects of mobilization with on shoulder range of motion and pressure pain threshold in people with painful limitation of shoulder movement. The results showed that the mobilization with movement reduced pain and improved range of motion.

Moreover, a randomized controlled trial conducted by Delgado et al showed that the short-term effects of mobilization with movement was effective to decrease pain intensity and increase shoulder range of motion. However, Guimarães et al compared the immediate effects of mobilization with movement with sham technique on shoulder range of motion, muscle strength and function in the patients with shoulder impingement syndrome. The results showed that the mobilization with movement was no more effective than sham technique in improving shoulder external rotation and abduction, pain and function. These different results lead this study to compare the effects of adding mobilization with movement on the conventional treatment.

Several outcomes have been commonly investigated in the shoulder impingement syndrome-related previous research, for example, pain intensity, shoulder range of motion, muscle strength, and shoulder function. The pain intensity was usually assessed using the visual analogue scale. The shoulder range of motion was assessed using a bubble inclinometer, the shoulder muscle strength, and function were investigated using hand held dynamometer (HHD) and a self-reported questionnaire e.g. shoulder pain and disability index, respectively.

MU-CIRB	Mahidol University Central Institutional Review Board (MU-CIRB)	Date Modified 02/08/2016
Mahidol University Centra	ll Institutional Review Board (MU Central-IRB) Study Protocol	Page 3 of 13

Since the postural correction exercise is commonly applied in the conventional physical therapy, neck and shoulder posture can be assessed using photogrammetry measurement. The neck and shoulder posture can be generally assessed by measuring the craniovertebral angle and shoulder angles, respectively.

#### 5. Objective of the Study

## 5.1 General Objective

To compare the effects of 4-week conventional physical therapy treatment (conventional group) with the conventional program and the addition of the mobilization with movement (mobilization with movement group) on pain intensity, shoulder, cervical and shoulder postures, shoulder muscle strength, and shoulder function in the patients with shoulder impingement syndrome.

# 5.2 Specific Objective

- 1) To compare the pain intensity between the conventional and the mobilization with movement groups at baseline, after intervention at week 1, week 2, week 3, and week 4.
- 2) To compare the shoulder range of motion between the conventional and the mobilization with movement groups at baseline, after intervention at week 1, week 2, week 3, and week 4.
- 3) To compare the craniovertebral angle and shoulder angles between the conventional and the mobilization with movement groups at baseline, after intervention at week 2, and week 4.
- 4) To compare the shoulder muscle strength between the conventional and the mobilization with movement groups at baseline, after intervention at week 2, and week 4.
- 5) To compare the shoulder pain and disability index scores between the conventional and the mobilization with movement groups at baseline, after intervention at week 2, and week 4.

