### 6.3 Sample size

Sample size calculation will be performed using formula for the test of different between 2 independent means.

According to the G\*power 3.1.9.2 program calculation, the total of this study equal 20 subjects. Based on the previous study using the shoulder pain and disability index to measure the shoulder function, in the study of comparing the immediate effects of mobilization with movement and sham techniques. The mean (standard deviation) between group post-intervention for the mobilization with movement group was 4.6 (5.0) and that for the sham group was 0.4 (1.1) (12). In this proposed study, we need equal number of participants per group; therefore, the drop out calculation of 20% from the total participants (n = 1/1-20%). Therefore, after the ethical approval, the researcher will collect data from 24 shoulder impingement syndrome patients (12 subjects on the conventional group and 12 subjects on the mobilization with movement group).

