## - Statistics to be used or process for data analysis

Data will be analysed by using SPSS version 23. The statistical significance level is set at p-value < 0.05.

- Shapiro-Wilk will be used to examine the distribution of the data
- Descriptive statistics for demographic data, mean and standard deviation for continuous, cumulative frequency for categorical and median for ordinal variables, will be calculated.
- Two-way mixed design ANOVA (two group x four time) for parametric data. If the data are significant the post hoc analysis will be performed using Bonferroni.
- Friedman test if the data are not normally distributed.

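### Baseline is listed as a between-group comparison in every objective but is never used as a covariate, and the ANOVA does not say whether baseline is one of its four times

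*Combined protocol and SAP*

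**What the plan says.** Section 5.2 (Specific Objective) gives five objectives, each a comparison between the two arms. For pain and range of motion the arms are compared as "groups at baseline, after intervention at week 1, week 2, week 3, and week 4". For posture, strength and SPADI they are compared as "groups at baseline, after intervention at week 2, and week 4". Baseline is therefore a listed between-group comparison in all five.

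Section 9 (Statistics to be used) plans a "Two-way mixed design ANOVA (two group x four time) for parametric data", followed by this rule: "If the data are significant the post hoc analysis will be performed using Bonferroni". The level is given as "The statistical significance level is set at p-value < 0.05", without sidedness. The four times are not named, the Bonferroni family is not defined, and no primary time point is stated. No covariate or other baseline adjustment appears anywhere. Section 6.2.5 says that allocation is randomised by sealed envelopes, with a grouping by age.

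**The concern.** In a randomised trial any baseline difference between arms is due to chance, so a significance test there says nothing about treatment. The useful role of the baseline value is to explain part of the spread in the follow-up values, and the plan does not give it that role.

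With 12 patients per arm this matters in two ways. Power is scarce, and a covariate that is already collected may recover some of it. Chance imbalance is also common: the standard error of a baseline difference is √(2/12) = 0.408 SD, so a difference beyond 0.5 SD (z = 0.5/0.408 = 1.22) arises in about 22% of such trials. The plan would test such a difference but names no covariate adjustment for it.

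**Working it through.** **Inputs.** Section 6.3 gives SPADI means (SD) of 4.6 (5.0) and 0.4 (1.1), a total of 20 before dropout, and 12 per arm enrolled. The correlation ρ between visits is not given; I assume 0.2 to 0.7, equal for all pairs of visits. The plan gives no effect size for VAS, so applying the SPADI figure to pain is also an assumption.

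**The plan's own figure.** Pooled SD = √((25 + 1.21)/2) = 3.62, and d = 4.2/3.62 = 1.160. With the "formula for the test of different between 2 independent means", one-sided α = 0.05 and 10 per group, noncentral-t power is 80.2%, which reproduces 20. Section 6.3 states neither power nor sidedness. Two-sided power is 68.9% at 10 per arm and 77.5% at 12. All figures below are two-sided.

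**Does the four-level time factor include baseline?**

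| Outcome | Times with baseline | Times without |
|---|---|---|
| Pain, range of motion | 5 | 4 |
| SPADI, strength, posture | 3 | 2 |

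Four fits pain and range of motion only with baseline left out. It fits the other three outcomes under neither count. Both readings therefore have to be checked.

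**Covariate against no covariate, week 4 alone, α = 0.05, 12 per arm.** Unadjusted: noncentrality 1.160 × √(12/2) = 2.84 on 22 df, power 77.5%. ANCOVA: effect d/√[(1 − ρ²)(1 + 1/(2n − 4))] on 2n − 3 df, where the second factor allows for chance imbalance. At ρ = 0.5 this is 1.160/√(0.75 × 1.05) = 1.307, noncentrality 3.20, power 86.3%.

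| ρ | 0.2 | 0.3 | 0.5 | 0.7 |
|---|---|---|---|---|
| ANCOVA power | 77.0% | 79.2% | 86.3% | 95.9% |
| Change from 77.5% | -0.5 | +1.7 | +8.8 | +18.4 |

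With 10 completers per arm: 68.9% unadjusted, and 67.8%, 70.1%, 78.2% and 91.3% with the covariate.

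**Reading A: baseline is a level (pain, 5 visits).** Suppose the effect builds linearly as 0, ¼, ½, ¾, 1 times d. The group main effect averages these to 0.5d = 0.580. At ρ = 0.5 the SD of a patient's mean is √((1 + 4 × 0.5)/5) = 0.775, so the standardised effect is 0.749 and power is 42%. Averaging weeks 1-4 only gives 0.725/0.791 = 0.917 and 57%. That difference is the dilution.

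The treatment test under this reading is the group × time interaction, with noncentrality (n/2)Σ(δₜ − δ̄)²/(1 − ρ). At ρ = 0.5 this is 6 × 1.160² × 0.625/0.5 = 10.1 on 4 and 88 df, about 69%. Simulation with 8,000 runs per setting agrees:

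| ρ | Gradual: interaction | Gradual: week-4 ANCOVA | Constant from week 1: interaction | Constant: week-4 ANCOVA |
|---|---|---|---|---|
| 0.3 | 52.6% | 78.6% | 65.7% | 78.8% |
| 0.5 | 68.9% | 85.9% | 81.2% | 86.2% |
| 0.7 | 91.0% | 95.7% | 96.5% | 95.8% |

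For SPADI (3 visits, gradual) the interaction has 54%, 69% and 90% against 79%, 86% and 96%.

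**Reading B: weeks 1-4 only (pain).** Baseline is discarded. With gradual build-up the group effect has 70%, 57% and 49% at ρ = 0.3, 0.5 and 0.7, and the interaction 32%, 42% and 65%. With a constant effect the interaction has about 5%, and the group effect carries the result (92.6% at ρ = 0.5).

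**Bonferroni.** If the family is the between-group tests by visit, removing baseline moves α for pain from 0.05/5 = 0.0100 to 0.05/4 = 0.0125, and week-4 power from 52.1% to 55.7% (+3.6). For SPADI, α moves from 0.05/3 = 0.0167 to 0.05/2 = 0.0250, and power from 60.3% to 66.9% (+6.6). These figures ignore the requirement that the ANOVA be significant first. If the two arms are compared separately within each visit, there is one comparison per visit and baseline costs nothing.

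**The case against.** A reader might infer that baseline certainly enters the ANOVA, that Bonferroni alpha is certainly spent on it, and that power at week 4 is roughly halved as a result. The documents do not support this.

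- Section 9 says four times. For pain, a primary outcome, that count matches the schedule only without baseline.
- The Bonferroni family is undefined, so the alpha cost is conditional, and it is modest even where it applies.
- The halving comes from setting the diluted main effect (42%), or a week-4 contrast at 0.01 that needs a significant interaction first, against a single week-4 ANCOVA at 0.05 (86%). These are not like for like. Testing week 4 alone at 0.05 without any covariate already gives 77.5%, so most of that gap comes from naming one time point.

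Three further points stand. Baseline as a level is not invalid: the interaction then tests differential change and takes account of a chance baseline difference. The covariate gain is about nil at ρ of 0.2 to 0.3, and the entry window of 4-7 cm on the VAS (section 6.2.1) may keep ρ low for pain. Week-4 ANCOVA is also not always the strongest test: with a constant effect, the group effect over weeks 1-4 beats it (92.6% against 86.2% at ρ = 0.5).

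None of this gives the baseline test a purpose or supplies the missing covariate.

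**Conclusion.** The point holds in limited form. The baseline comparisons in section 5.2 answer no treatment question, and under either reading of the time factor the baseline value is not used as a covariate. The time factor itself does not match the schedules in section 5.2.

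Against an unadjusted week-4 test, the covariate is worth between about -0.5 and +18 points of power. Against the interaction with baseline as a level and a gradual effect, week-4 ANCOVA gains about 26, 17 and 5 points at ρ = 0.3, 0.5 and 0.7, with little or no gap if the effect is constant from week 1 and ρ is high. The alpha cost is about 4 points of power for pain and 7 for SPADI, and only with a by-visit family.

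These sizes rest on an assumed ρ, equal correlation between visits, 12 analysed per arm, and d = 1.16, which comes from an immediate-effect comparison with sham on SPADI. This is an inexpensive gain in efficiency and clarity; the planned analysis is not invalid because of it.

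**What to change.** In section 5.2, remove baseline from the between-group comparisons and say that baseline values will be described by arm without a test.

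In section 9:
- Name week 4 as the primary time point. It is the end of the programme and a visit shared by all five outcomes.
- Compare the arms at week 4 with the baseline value of the same outcome as covariate. Use ANCOVA, or a mixed model of the post-baseline visits with baseline and the age grouping used in allocation as covariates.
- State the time levels separately for each outcome: weeks 1-4 for pain and range of motion, weeks 2 and 4 for SPADI, strength and posture.
- Report the earlier visits as supportive.

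The cost is wording in two sections. Baseline is already measured for every outcome, and SPSS, the planned software, fits these models.

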## 6. Research Plan

### 6.1 Type of Research

Biomedical / Clinical Research

✓ Procedural / intervention

Conventional physical therapy, Postural correction exercise, & Mobilization with movement

# 6.2 Subject selection and allocation

#### 6.2.1 Inclusion criteria

- 1) Age 20-60 years old
- 2) Anterior and/or lateral shoulder pain (between acromion and glenoid)
- 3) Score 4-7 cm on the 0-10 visual analogue scale (VAS)

MU-CIRB	Mahidol University Central Institutional Review Board (MU-CIRB)	Date Modified 02/08/2016
Mahidol University Centra	l Institutional Review Board (MU Central-IRB) Study Protocol	Page 4 of 13

- 4) Experienced shoulder pain at least 3 months
- 5) Positive combination 2 of 3 impingement tests (Painful arc, Empty can, and External rotation test)
- 6) Negative at least one of rotator cuff tear test (Isometric infraspinatus and subscapularis muscle tests)

There is no different between dominant hand and non-dominant in case of functional assessment, because some of the SPADI question ask the function that required both hand activity and the severity of the involved hand). If the patient has bilateral shoulder impingement syndrome they will be excluded because if the patient had bilateral impingement syndrome, it will affect the scapular motion and scapulothoracal joint on the both sides.

#### 6.2.2 Exclusion criteria

- 1) History of shoulder, cervical, or thoracic surgery
- 2) History of neurological conditions (stroke, brachial plexus injury)
- 3) Postural deformity and musculoskeletal condition that affect the shoulder movement
- 4) History of shoulder major trauma on the affected side (fracture, dislocation, tendon rupture and/or labral torn)
- 5) Having bilateral shoulder impingement syndrome
- 6) Recently using muscle relaxants, pain killer, or corticosteroid injection
- 7) Ligamentous laxity based on positive sulcus sign
- 8) Numbness or tingling in upper extremity
- 9) Systemic illness or widespread pain
- 10) Rheumatic disease
- 11) Having malfunction of rotator cuff muscle (e.g. cannot perform at all)
- 12) Having a passive limitation due to adhesive capsulitis
- 13) Positive of scapular retraction test

#### **6.2.3 Withdrawal criteria** (for individual participant)

- 1) Unwilling to follow the procedure
- 2) Unwilling to participate in this study
- 3) Unable to participate until the process complete
- 4) Participants with any uncomfortable condition can quit in any session

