## 6.4 Replacement procedure if subject withdraw from the study

not necessary because the number of subjects calculated already include drop out number

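### Stopping or refusing treatment counts as leaving the study, and the planned tests drop incomplete records, so the comparison may not be of the randomised groups

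*Combined protocol and SAP*

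**What the plan says.** Section 6.2.3 gives four grounds for withdrawing an individual. The first is "Unwilling to follow the procedure". The second, listed separately, is unwillingness to take part in the study. The third is being unable to stay to the end. The fourth is "Participants with any uncomfortable condition can quit in any session".

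Section 6.4 says that replacing withdrawn participants is "not necessary because the number of subjects calculated already include drop out number". Section 6.3 allows for 20% drop-out and recruits 24, 12 per group.

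In section 9, pain on the VAS and shoulder function on the SPADI are both primary outcomes. The analysis is "Two-way mixed design ANOVA (two group x four time) for parametric data", with "Friedman test if the data are not normally distributed". The software is SPSS 23 and the significance level is 0.05.

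Section 5.2 compares pain at baseline and weeks 1, 2, 3 and 4, and SPADI at baseline and weeks 2 and 4. No visible text names an analysis set, a missing-data method or any assessment after treatment stops.

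**The concern.** Because the first and second criteria are separate, a participant who declines the treatment but is still willing to be measured has the same status as one who leaves altogether. Nothing in the plan then asks for that person's later outcomes.

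The analysis makes the loss larger. A repeated-measures ANOVA in standard form needs a value at every time point, and so does the Friedman test. A participant who stops after week 2 therefore contributes nothing, although baseline, week 1 and week 2 pain were recorded.

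Reasons for stopping may be related to both outcome and arm. Pain is a primary outcome, discomfort is a named exit route, and only one arm receives the added manual technique. If those who leave differ between arms, randomisation no longer protects the comparison of those who remain. With 12 per arm, one or two such exits are enough to matter.

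**Working it through.** **1. The plan's own figures.** Section 6.3 uses means (SD) of 4.6 (5.0) and 0.4 (1.1).

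- Pooled SD = √((5.0² + 1.1²)/2) = 3.62, and d = 4.2/3.62 = 1.16.
- A one-sided 5% t-test with 80% power needs 9.94, so 10 per arm. This reproduces the stated total of 20. Sidedness and power are not stated; a two-sided test would need 13 per arm.
- 20 × 1.2 = 24, the stated recruitment. Dividing by 1 − 0.20 would give 25. That difference does not affect this point.
- Expected loss: 0.20 × 24 = 4.8 participants, or 0.20 × 12 = 2.4 per arm.

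**2. Who enters the analysis.**

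- *Stops treatment, willing to be measured:* withdrawn under the first or fourth criterion; no later assessment described; incomplete record; dropped by the ANOVA and by Friedman.
- *Withdraws consent:* withdrawn under the second criterion; later data cannot be collected under any wording; dropped in the same way.
- *Completes all visits:* analysed.

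The first group is the one that a change of rule could recover.

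**3. Illustrative size of the bias.** The documents give no VAS standard deviation and no expected pattern of drop-out, so everything here is an assumption: no true effect, normal outcomes, 12 per arm, loss from the mobilization arm only, and leavers chosen by a score that correlates with final pain at 0.3, 0.5 or 1.0. A two-sided 5% t-test stands in for the group comparison.

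| Lost from mobilization arm | Correlation 0.3 | Correlation 0.5 | Correlation 1.0 |
|---|---|---|---|
| 2 of 12: shift; type I error | 0.08 SD; 5.5% | 0.14 SD; 6.4% | 0.27 SD; 11% |
| 3 of 12: shift; type I error | 0.12 SD; 5.8% | about 0.20 SD; 7.3% | 0.40 SD; 17% |

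As a check on the first row: shift = (number lost/12) × (gap in mean between leavers and stayers). When the two worst of 12 always leave, the mean gap is 1.65 SD, so the shift is (2/12) × 1.65 ≈ 0.27 SD. At correlation 0.3 it is 0.3 × 0.27 ≈ 0.08 SD.

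In the right-hand column, part of the excess rejection arises because trimming the extremes also shrinks the observed SD.

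**4. Power.** At d = 1.16, two-sided power is 0.69 with 10 per arm and 0.78 with 12. This assumes the same effect in those who stop treatment; a smaller effect in them would reduce the gain.

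**The case against.** The strongest reply is that the plan is silent on these matters and does not lay down a harmful rule. Much of that stands.

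- A reader might infer that outcome collection after withdrawal is ruled out. Section 6.2.3 does not say so. It is a short list that neither provides for later assessment nor forbids it. The flow chart's content and the consent pages are not in the text available, and either might address it.
- A reader might infer that only those who tolerated treatment are analysed. The first criterion concerns willingness and could include refusing assessments. Tolerability enters through the fourth criterion, which is the participant's right to quit and must stay.
- The restriction to complete records is not written in the plan. It follows from the named methods in standard form, with no other missing-data approach given.
- A reader might put the harm higher, for instance by taking two leavers each 3 cm worse with an SD of 1.5 cm: (2/12) × 3 = 0.5 cm, or 0.33 SD, and a type I error of about 12%. Neither input is in the documents. The 0.33 SD needs a gap of 2 SD, more than the 1.65 SD obtained on average when the two worst of 12 always leave.
- A further loss of complete cases through missed visits, on top of the 20%, is also unsupported. That 20% may already include incomplete records.
- Both arms receive conventional therapy. If they lose similar patients, the average shift largely cancels.

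What the reply does not remove is that non-adherence is a stated ground for withdrawal, separate from refusing the study, and that the named tests then discard the person's record.

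**Conclusion.** The point holds as a design weakness that is cheap to correct. Followed as written, the plan can lose participants who stop treatment but would still be willing to be measured, and the planned tests discard what they had already contributed. The result may then compare selected subsets of the randomised groups.

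Neither the size nor the direction of the bias is known. Under the one-arm scenario with 2 of 12 lost, about 0.08 to 0.27 SD and a type I error of about 5.5% to 11% is a reasonable range. It depends on loss being one-sided and related to pain. The documents do not show that either will happen.

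**What to change.** - **Section 6.2.3:** separate stopping study treatment from withdrawing consent to follow-up, and leave the right to withdraw from either intact. State that willing participants who stop treatment will be asked for the primary outcomes at the remaining visits, at least week 4. SPADI could be given by telephone. The VAS is rated during shoulder abduction (sections 7 and 8), so it needs an attended visit.
- **Section 6.4:** report treatment stops and study withdrawals separately, by arm and with reasons.
- **Section 9:** analyse all randomised participants in their assigned group with a linear mixed model using all available visits, in place of the ANOVA. The Friedman fallback would bring back the need for complete records, so it should not carry the primary comparison.

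The cost is protocol and consent wording and a few extra contacts or visits within four weeks. There are two limits. The estimate will include participants who did not complete treatment. The mixed model does not remove bias if leaving depends on pain that was never observed, which is why the collection rule needs to change as well as the analysis.
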